10.3.1.1.6. Gastrointestinal Perforation

An infrequent incidence of gastrointestinal (GI) perforations has been associated with some antiangiogenic therapeutic agents, most specifically in the context of colorectal cancer and in advanced ovarian cancer. Gastrointestinal perforation has been reported from clinical studies investigating ramucirumab, although no events of GI perforation were observed in REACH.

Discontinue study treatment if the patient experiences a GI perforation ([Table JVDE.3](#)).

10.3.1.1.7. Reversible Posterior Leukoencephalopathy Syndrome

Reversible posterior leukoencephalopathy syndrome (RPLS) is a clinical and radiologic syndrome typically consisting of reversible cortical neurological dysfunction and brain-imaging findings of subcortical edema involving the posterior circulation, particularly the occipital lobes (Hinchey et al. 1996).

Across the clinical program to date, 2 cases of RPLS have been reported. Both cases occurred in the study evaluating ramucirumab in combination with chemotherapy for patients with metastatic colorectal cancer. No RPLS events were observed in REACH.

Symptoms of RPLS most often include generalized seizures, headache, delirium, and cortical blindness, although these may vary significantly and occasionally include focal neurological deficits (Hinchey et al. 1996; Garg 2001; Lee et al. 2008). MRI represents the most reliable method for diagnosis (Lee et al. 2008).

Discontinue study treatment if the patient experiences RPLS ([Table JVDE.3](#)).

10.3.1.1.8. Congestive Heart Failure

An increased risk of congestive heart failure (CHF) has been associated with some antiangiogenic therapeutic agents, particularly in patients previously treated with anthracyclines. A small number of CHF events (including fatal) were also reported in patients who had received ramucirumab after prior treatment with anthracyclines. In REACH, no events of CHF were observed in the ramucirumab arm.

Patients with risk factors should be closely monitored for signs and symptoms of CHF. Caution should be exercised when treating patients with clinically significant cardiovascular disease, such as preexisting coronary artery disease or CHF.

Discontinue study treatment if the patient experiences any Grade 3 or 4 events consistent with CHF ([Table JVDE.3](#)).

10.3.1.1.9. Fistula Formation

Fistula formation has been associated with antiangiogenic agents and patients may be at an increased risk for the development of fistula when treated with ramucirumab. Fistula has been reported from clinical studies investigating ramucirumab, although no events of fistula were observed in REACH.

Discontinue study treatment if the patient experiences a fistula ([Table JVDE.3](#)).

10.3.1.1.10. Surgery and Impaired Wound Healing

Because ramucirumab is an antiangiogenic therapy, it may have the potential to adversely affect wound healing. Ramucirumab did not impair wound healing in a study conducted in animals; however, the impact of ramucirumab on serious or nonhealing wounds has not been evaluated in humans. In REACH, no wound healing complications were observed in the ramucirumab arm.

Withhold study treatment prior to any planned surgery ([Table JVDE.3](#)). In the event of postsurgical or other wound complications, delay study treatment until the wound is fully healed.

After surgery, resume study treatment based on clinical judgment. Delay ramucirumab dosing (for up to 21 days) in the case of any post-surgical or other wound complications until the wound is fully healed.

10.3.1.1.11. Liver Failure and Other Significant Liver Injury

Liver failure or other significant liver injury events, such as hepatic encephalopathy, have been observed in patients with advanced HCC receiving ramucirumab.

In REACH, the incidence of any-grade liver failure / liver injury events, including clinical and laboratory events, was higher in the ramucirumab arm (50.5%) compared with the placebo arm (37.3%). Any-grade clinical events reported at a higher rate in the ramucirumab arm included hepatic encephalopathy and ascites. There was no difference in the incidence of Grade 3/4 liver failure/injury in the ramucirumab arm (19.1%) compared with the placebo arm (22.5%). No Grade 5 events of hepatic encephalopathy or ascites were observed.

Discontinue study treatment if the patient experiences hepatic encephalopathy and/or hepatorenal syndrome ([Table JVDE.3](#)).

10.3.1.2. Serious Adverse Events

An SAE is any adverse event from this study that results in one of the following outcomes:

- death
- a life-threatening experience (that is, immediate risk of dying)
- persistent or significant disability/incapacity
- initial or prolonged inpatient hospitalization
- congenital anomaly/birth defect
- considered significant by the investigator for any other reason

Important medical events that may not result in death, be life-threatening, or require hospitalization may be considered serious adverse drug events when, based upon appropriate medical judgment, they may jeopardize the patient and may require medical or surgical intervention to prevent one of the outcomes listed in this definition.

Serious adverse event collection begins after the patient has signed informed consent and has received study treatment. If a patient experiences an SAE after signing informed consent, but prior to receiving study treatment, the event will not be reported as serious unless the investigator feels the event may have been caused by a protocol procedure.

Data on SAEs that occur before the end of trial will be stored in the collection database and the Lilly Safety System.

Study site personnel must alert Lilly or its designee of any **serious** adverse event (SAE) within 24 hours of investigator awareness of the event via a sponsor-approved method. If study site personnel contact Lilly or its designee by telephone regarding an SAE, study site personnel must also immediately provide official notification on study-specific SAE forms.

This 24-hour notification requirement refers to the initial SAE information and all follow-up SAE information.

Planned surgeries should not be reported as SAEs unless the underlying medical condition has worsened during the course of the study.

Planned hospitalizations or procedures for preexisting conditions that are already recorded in the patient's medical history at the time of study enrollment should not be considered SAEs. Hospitalization or prolongation of hospitalization without a precipitating clinical AE (for example, for the administration of study treatment or other protocol-required procedure) should not be considered SAEs.

Serious adverse events due to disease progression, including death, should not be reported unless the investigator deems them to be possibly related to study treatment.

The investigator does not need to actively monitor patients for AEs once the trial has ended, unless provided otherwise in the protocol; however, if an investigator becomes aware of an SAE occurring after the patient's participation in the trial has ended, and the investigator believes that the SAE is related to a protocol procedure or study treatment, the investigator should report the SAE to Lilly, and the SAE will be entered in the Lilly Safety System.

Information on SAEs expected in the study population independent of drug exposure and that will be assessed by Lilly in aggregate periodically during the course of the trial may be found in the IB.

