10.3. Safety Evaluations

Investigators are responsible for monitoring the safety of patients who have entered this study and for alerting Lilly or its designee to any event(s) that seems unusual, even if this event(s) may be considered an unanticipated benefit to the patient.

The investigator is responsible for the appropriate medical care of patients during the study.

The investigator remains responsible for following, through an appropriate health care option, AEs that are serious, considered related to the study, or that caused the patient to discontinue before completing the study. The patient should be followed until the event is resolved or explained. Frequency of follow-up evaluation is left to the discretion of the investigator.

The timing of all safety evaluations is shown in the study schedule ([Attachment 1](#)) and the continued access study schedule ([Attachment 2](#)). [Table JVDE.6](#) presents a summary of AE and SAE reporting guidelines for every period of this study – at baseline, during study treatment, during short- and long-term follow-up, and during continued access. [Table JVDE.6](#) also shows the database or system is used to store AE and SAE data.

Table JVDE.6. Adverse Event and Serious Adverse Event Reporting Guidelines

Period	Types of AEs/SAEs to be Reported	Collection Database	Lilly Safety System
Baseline	Preexisting conditions	x	
	All AEs	x	
	SAEs related to protocol procedures	x	x
Study treatment period	All AEs	x	
	All SAEs	x	x
Short-term postdiscontinuation follow-up	All AEs	x	
	All SAEs	x	x
Long-term postdiscontinuation follow-up	All SAEs related to protocol procedures or study treatment	x	x
Continued access period	All AEs	x	
	All SAEs	x	x
Continued access follow-up	All AEs	x	
	All SAEs	x	x
After the patient is no longer participating in the study (that is, no longer receiving study treatment and no longer in follow-up)	All SAEs related to protocol procedures or study treatment that the investigator becomes aware of		x

Abbreviations: AEs = adverse events; SAEs = serious adverse events.

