10.3.1. Adverse Events

Lilly has standards for reporting AEs that are to be followed regardless of applicable regulatory requirements that may be less stringent. A clinical study AE is any untoward medical event associated with the use of a drug in humans, whether or not it is considered related to that drug.

Lack of drug effect is not an AE in clinical trials, because the purpose of the clinical trial is to establish drug effect.

Any clinically significant findings from electrocardiograms (ECGs), labs, vital sign measurements, or other procedures that result in a diagnosis should be reported to Lilly or its designee.

Cases of pregnancy that occur during maternal or paternal exposures to ramucirumab or placebo should be reported. Data on fetal outcome and breast-feeding are collected for regulatory reporting and drug safety evaluation.

Study site personnel will record the occurrence and nature of each patient's preexisting conditions, including clinically significant signs and symptoms of the disease under treatment in the study.

After the ICF is signed, site personnel will record the occurrence and nature of any AEs and any change in the preexisting conditions. All AEs related to protocol procedures are reported to Lilly or its designee.

In addition, all AEs occurring after the patient receives the first dose of ramucirumab or placebo must be reported to Lilly or its designee via the CRF.

Investigators will be instructed to report to Lilly or its designee their assessment of the potential relatedness of each AE to protocol procedure or study treatment via the CRF.

The investigator will decide whether he or she interprets the observed AEs to be related to the study treatment or study procedure. To assess the relationship of the AE to study treatment or study procedure, the following terminologies are defined:

- **Probably related:** a direct cause and effect relationship between study treatment and the AE is likely
- **Possibly related:** a cause and effect relationship between the study treatment and the AE has not been demonstrated at this time and is not probable, but is also not impossible
- **Does not know:** the investigator cannot determine
- **Not related:** without question, the AE is definitely not associated with the study treatment

The investigator should classify all “probably related,” “possibly related,” or “does not know” AEs and SAEs as related to study treatment or study procedure.

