12.2.13. Interim Analyses

An IDMC will be established as an oversight mechanism to monitor overall study conduct. The membership, roles and responsibilities for the IDMC are defined in the IDMC Charter.

Regular safety reviews will be conducted by the IDMC. There will be no prespecified rules for stopping or modifying the trial due to safety concerns. The IDMC members will review unblinded safety data at each interim analysis to determine whether there are sufficient safety concerns to justify modifying the study or the termination of study treatment and/or enrollment. The first 2 safety interim analyses are planned to be performed when approximately 50 and 150 patients have received 3 cycles of study treatment, died, or discontinued study treatment. Thereafter, safety review will be conducted twice annually, or as requested by the IDMC.

No efficacy interim analysis is planned for this study.

Only the IDMC is authorized to evaluate unblinded interim analyses. Study sites will receive information about interim results ONLY if they need to know for the safety of their patients. Details on the process flow/communication plan are provided in the IDMC Charter.

Patient enrollment will continue during data assessment by the IDMC.

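### The protocol gives two conflicting rules for SAEs attributed to disease progression, so serious liver and bleeding events can be under-counted in SAE outputs

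*Protocol*

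**What the plan says.** Protocol Section 10.3.1.2 lists death among the outcomes that make an event serious. It sets the notification duty without qualification: "Study site personnel must alert Lilly or its designee of any" serious adverse event within 24 hours of awareness. It adds that data on SAEs before the end of trial are stored in both the collection database and the safety system. The same section then says: "Serious adverse events due to disease progression, including death, should not be reported unless the investigator deems them to be possibly related" to study treatment.

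Section 10.3 introduces Table JVDE.6 as a table that "presents a summary of AE and SAE reporting guidelines for every period of this study". For the treatment period, short-term follow-up, continued access and continued access follow-up, its rows call for all SAEs in both systems. No footnote excepts events due to progression.

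On AEs in general, Section 10.3.1 says that "all AEs occurring after the patient receives the first dose of ramucirumab or placebo must be reported to Lilly or its designee" via the CRF. It defines not related as "without question, the AE is definitely not associated with the study treatment", and tells investigators to class events of possible or unknown relationship as related.

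Bleeding and liver failure/injury are both AESIs (Sections 9.4.2, 10.3.1.1.5 and 10.3.1.1.11). On the earlier Phase 3 trial, Section 10.3.1.1.11 notes: "Any-grade clinical events reported at a higher rate in the ramucirumab arm included hepatic encephalopathy and ascites".

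**The concern.** A site that follows the table reports a serious hepatic or bleeding event that the investigator attributes to progression. A site that follows the later sentence of Section 10.3.1.2 does not. In advanced hepatocellular carcinoma, encephalopathy, ascites, liver failure and bleeding can come from the disease and are also the events watched for with the drug, and the exemption makes no exception for AESIs. Whether such an event counts as an SAE then depends on the investigator's attribution and on which rule the site applies.

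The outputs at stake are the SAE tables (SAP 6.5.6.4), the SAE lines of the overall AE summary (SAP 6.5.6.2), the registry SAE summary (SAP Appendix 2) and the sponsor safety system. The filter also acts through progression, which occurs after randomization and on which the earlier trial showed a treatment effect (Protocol Section 5). Equal filtering in the two arms therefore cannot be taken for granted, even under blinding.

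**Working it through.** The plan states no figure for this point, so there is nothing to reproduce. The check compares the texts and then illustrates scale.

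**1. Is the table loose shorthand?** It restricts SAEs where it means to: to procedure-related events at baseline, and to events related to procedures or treatment in long-term follow-up and after participation. Its unrestricted rows therefore read as deliberate. The sentence in Section 10.3.1.2 itself calls the progression events SAEs and then exempts them. The two rules cannot both be followed.

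**2. What does not being reported cover?** The protocol does not say.
- If it means SAE reporting only, the event stays on the CRF as an AE. It still enters the TEAE tables (SAP 6.5.6.3) and the AESI summary and listing (SAP 6.5.6.4), which are not restricted to serious events. Only the SAE outputs under-count.
- If a site takes it to mean no CRF record, the AE and AESI summaries lose the event too.
- On either reading, deaths are collected for overall survival, and laboratory results are graded on numeric values alone (SAP 6.5.6.5.1).

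**3. Scale.** Inputs: planned arms of 186 and 93 (Protocol 12.1); earlier-trial Grade 3/4 liver failure/injury of 19.1% vs 22.5% (10.3.1.1.11); Grade 3 or higher bleeding of 6.1% vs 7.6% (10.3.1.1.5). Assumptions not in the documents: these rates carry over, every such event is serious, and a fraction f is attributed to progression and not reported.

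Patients with events = arm size × rate:
- Liver: 186 × 0.191 = 35.5; 93 × 0.225 = 20.9
- Bleeding: 186 × 0.061 = 11.3; 93 × 0.076 = 7.1

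Missing from SAE outputs = arm size × rate × f (ramucirumab, placebo):

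| f | Liver | Bleeding |
|---|---|---|
| 0 | 0, 0 | 0, 0 |
| 0.25 | 8.9, 5.2 | 2.8, 1.8 |
| 0.50 | 17.8, 10.5 | 5.7, 3.5 |
| 0.75 | 26.6, 15.7 | 8.5, 5.3 |

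**4. Comparison between arms.** With equal f the ratio of rates is unchanged and only the absolute SAE rates fall. With unequal f it moves either way:
- 25% withheld on ramucirumab and 50% on placebo: 19.1 × 0.75 = 14.3% vs 22.5 × 0.50 = 11.3%, which reverses the order.
- 50% and 25%: 19.1 × 0.50 = 9.6% vs 22.5 × 0.75 = 16.9%.

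These two cases show sensitivity only. The documents give no basis for choosing between them.

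**The case against.** The strongest reply is that the table calls itself a summary, that Section 10.3.1.2 is the detailed rule, and that a general duty followed by exceptions is not a contradiction. The table also omits that section's exceptions for planned surgery and planned hospitalization. This stands only in part. Those exceptions say what does not count as an SAE, whereas the progression sentence withholds events that it accepts are SAEs.

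The second reply is that the filter is narrow and the safety data have other routes. This stands. An investigator who is unsure whether drug or disease caused an event must class it as related, so it falls outside the exemption. All AEs after first dose go on the CRF. Hospitalizations due to AEs are summarized (SAP 6.5.6.6), deaths are summarized by reason with study disease as a category (SAP 6.5.6.4), and the sponsor reviews all deaths blinded (Protocol 10.3.3).

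A reader might infer that liver and bleeding events drop out of the safety signal, or that the IDMC would not see them. The documents do not support either inference. The AE and AESI routes remain open on the narrower reading. Protocol 12.2.13 says only that "The IDMC members will review unblinded safety data at each interim analysis", and SAP 6.6 refers to selected tables and listings. Neither ties the IDMC to SAE tables.

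A reader might also infer that the exemption dilutes a difference already shown, citing any-grade liver events of 50.5% vs 37.3% (13.2 points) or any bleeding of 32.5% vs 19.9% (12.6 points). Those are any-grade AE incidences, and the liver figure includes laboratory events. At the severe grades the earlier trial showed no ramucirumab excess.

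**Conclusion.** The conflict is real and should be resolved. Its supported consequence is possible under-counting of serious liver failure/injury and bleeding events in the SAE tables, the registry SAE summary and the safety system, varying with investigator attribution and with the rule a site follows. Loss from the AE and AESI summaries follows only if a site reads the exemption as covering CRF recording, a reading that the wording leaves open.

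The size is unknown. At the earlier trial's Grade 3/4 liver rates, with all such events assumed serious, the ceiling is about 36 of 186 and 21 of 93 patients, and about 18 and 10 if half are attributed to progression. The broad definition of relatedness should keep the true number below the ceiling. Neither the fraction attributed to progression nor its balance between arms can be derived from the documents.

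**What to change.** Reconcile Section 10.3.1.2, including its 24-hour rule, with Table JVDE.6, and state the same rule in both places:
- Every event that meets a seriousness criterion and an AESI definition, at least for liver failure/injury and bleeding, is recorded on the CRF and counted as an SAE whatever its attributed cause.
- Attribution to progression is captured as a field and not used as a filter.
- The exemption is kept only for disease progression itself as the event term.

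The seriousness condition matters. Without it, at the earlier trial's any-grade liver rates, SAE forms would be needed for about 0.505 × 186 + 0.373 × 93 = 129 of 279 patients, including non-serious laboratory findings.

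The cost is protocol wording and a limited number of additional SAE forms at sites. No efficacy analysis changes.

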10.3.1.3. Suspected Unexpected Serious Adverse Reactions

Suspected unexpected serious adverse reactions (SUSARs) are serious events that are not listed in the Development Core Safety Information in the IB and that the investigator identifies as related to study treatment or study procedure. United States 21 CFR 312.32 and European Union Clinical Trial Directive 2001/20/EC, and the associated detailed guidances or national regulatory requirements in participating countries, require the reporting of SUSARs. Lilly has procedures that will be followed for the recording and expedited reporting of SUSARs that are consistent with global regulations and associated detailed guidances.

10.3.2. Other Safety Measures

10.3.2.1. Electrocardiograms

For each patient, 12-lead digital ECGs will be collected according to the study schedule ([Attachment 1](#)) as single ECG. The patient must be supine for approximately 5 to 10 minutes before ECG collection and remain supine but awake during ECG collection. ECGs are recommended to be recorded before collecting any blood for safety or PK tests. ECGs may be obtained at additional times, when deemed clinically necessary. All ECGs recorded should be stored at the investigational site.

ECGs will be interpreted by a qualified physician (the investigator or qualified designee) at the site as soon after the time of ECG collection as possible, and ideally while the patient is still

present, to determine whether the patient meets entry criteria and for immediate patient management, should any clinically relevant findings be identified.

After enrollment, if a clinically significant finding is identified (including but not limited to changes in QT/corrected QT interval from baseline), the investigator will determine if the patient can continue in the study. The investigator or qualified designee is responsible for determining if any change in patient management is needed and must document his/her review of the ECG printed at the time of collection. Any new clinically relevant finding should be reported as an AE.

10.3.2.2. Echocardiogram or Multiple-Gated Acquisition Scan

An echocardiogram or multiple-gated acquisition scan will be performed according to the study schedule ([Attachment 1](#)). Additional evaluations are not required but should be performed in the setting of cardiac symptoms, at the discretion of the investigator.

